## **17.2 Sample size**

### **Primary Outcome**

The original target for the PRINCESS trial was to randomise 330 participants from around 20 care homes in Wales and England. This would provide 90% power at the 5% level to demonstrate a 10% relative reduction in cumulative antibiotic administration days (CAAD) (assuming an average CAAD of 17.4 days and an absolute reduction in the probiotic arm to 15.6 days per resident-year). We consider that a 10% reduction is feasible and would be clinically important.

This sample size accounted for 30% of participants being lost to follow-up due to withdrawal or death during the study.

An interim assessment of primary outcome ascertainment revealed that the mean percentage of days for which there are valid antibiotic administration data (i.e. either no antibiotics administered, or the number of days antibiotics have been administered in a given week) is 77.4%, or 283 days out of a possible 365 on average. This percentage varies depending on the length of time participants have been in the study. However, it remains high for participants who have been in the study for over six-months, and does not take into account other data sources that might be used (e.g. hospital discharge summaries, medication administration records, etc.). This is likely to therefore reflect an underestimate of the availability of primary outcome data, but nevertheless is a more accurate reflection of the likely level of follow-up when compared to our original assumption.

Given slower than anticipated recruitment, and this new information regarding the trade-off between the number of participants required and average length of follow-up, we will aim to randomise between 258 and 270 participants. Assuming a mean number of days for which primary outcome data will be available (i.e. accounting for follow-up time and missing data) of approximately 250 days, this will provide at least 82% power to detect a 10% relative reduction in CAAD.

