## **18 Analysis**

### **18.1 Main analysis**

The primary analysis will be by intention-to-treat, and will consist of a between-group comparison of the mean cumulative antibiotic administration days (CAAD) using Poisson regression. As the randomisation will be stratified by care home, the regression model will control for the care home a participant was recruited from. Negative binomial regression will be used in the presence of over-dispersed count data.

For secondary outcomes, depending on the type of data, a mixture of Poisson, linear, logistic and Cox models will be used to appropriately compare trial arms with respect to rates, means, proportions and time to events (see table below for more details).

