## 18.2 Description of outcomes and method of statistical analysis

Outcome	Main analysis	Sensitivity analyses*
Primary		
Cumulative antibiotic administration days (CAAD)	Poisson regression.	Negative binomial regression (if Poisson over-dispersed).
Secondary		
CAAD by infection (UTI, RTI, skin, GI, unexplained fever)	Poisson regression, with trial arm interacted with infection.	Negative binomial regression (if Poisson over-dispersed).
Incidence of infection	Poisson regression.	Negative binomial regression (if Poisson over-dispersed).
Site of infection	Poisson regression, with trial arm interacted with infection.	Negative binomial regression (if Poisson over-dispersed).
Mean duration of infection	A two-level Cox PH (frailty) model with infections nested within participants.	
Cumulative number of infection days	Poisson regression.	Negative binomial regression (if Poisson over-dispersed).
Antibiotic-associated diarrhoea Incidence and duration	Poisson regression.	Negative binomial regression (if Poisson over-dispersed).
All- cause diarrhoea (incidence and cumulative days)	Poisson regression.	Negative binomial regression (if Poisson over-dispersed)
Mean duration of diarrhoea episodes	A two-level Cox PH (frailty) model with infections nested within participants.	
Secondary – Health Utility		
Health utility (EQ5D)	Two linear regressions (EQ5D at 3/12 months separately) controlling for baseline EQ5D.	Transformations for normality.
Well-being (ICECAP-O)	Two linear regressions (ICECAP-O at 3/12 months separately) controlling for baseline ICECAP-O.	Transformations for normality.
Hospital stays	Logistic regression.	Poisson/negative binomial regression of counts (mean rate of hospital stays).
Death	Logistic regression.	Cox PH model for time from randomisation to death.
Secondary - Antimicrobial		

Resistance		
Presence of Gram-negative isolates in stools	Two logistic regression (stool sample finding at 3/12 months separately) controlling for baseline stool sample finding.	
Vancomycin resistant enterococci in stools	Two logistic regressions (stool sample finding at 3/12 months separately) controlling for baseline stool sample finding.	
Secondary - Mechanistic		
Immune parameters -Immune cell phenotypes -TLR ligand stimulated cytokines/chemokines -Plasma cytokines/chemokines -Monocyte and neutrophil phagocytosis -Flu vaccine response	Linear regression.	Transformation for normality.

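### The two arm-by-infection-type count models name no robust or within-resident variance, so the interaction test for antibiotic days is unreliable under both the Poisson model and its negative binomial fallback

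*Protocol*

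**What the plan says.** The table in section 18.2 gives the same main analysis for CAAD by infection (urinary, respiratory, skin, gastrointestinal, unexplained fever) and for site of infection: "Poisson regression, with trial arm interacted with infection". The sensitivity column for both rows lists negative binomial regression, conditional on over-dispersion. Section 18.1 puts the fallback more firmly: "Negative binomial regression will be used in the presence of over-dispersed count data". The only model control that section 18.1 names is care home.

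For mean duration of infection, the same table specifies "A two-level Cox PH (frailty) model with infections nested within participants", and it repeats that model for duration of diarrhoea episodes. No comparable wording appears in the two arm-by-type rows.

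**The concern.** To interact arm with infection type, the data must hold one count per resident per type, so five rows per resident. A frail resident is likely to be high on several of them. Antibiotic days also arrive in whole courses, so their variance is far above the Poisson variance. A model-based Poisson standard error allows for neither feature. A negative binomial model allows for extra variance in each row but still treats a resident's rows as independent.

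The interaction test asks whether the probiotic effect differs between infection types. If its error bars are wrong, the trial could report differences between types that are not there, or miss real ones. The two documented places for negative binomial (sensitivity column in 18.2, used when needed in 18.1) leave open which of the two models would be reported.

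**Working it through.** **Inputs from the protocol.** 258 residents, 1:1, about 250 days each (17.1, 17.2); 17.4 antibiotic days per resident-year (17.2); 2.16 courses per resident-year, split 47% respiratory, 29% urinary, 18% skin (4.2). Days per course: 17.4 / 2.16 = 8.06.

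**Assumptions.** Frailty variances and their shared part, varied below. Gastrointestinal infection and fever at 3% each in the five-type runs.

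**The protocol's own figure.** It gives none for these models. Its primary sample size reproduces as a pure Poisson comparison: n per arm = (1.96 + 1.2816)² × (17.4 + 15.66) / 1.74² = 115, and 230 / 0.7 = 329 against the stated 330. For 129 per arm and 250 days, power is about 81% with 15.66 and 84% with the rounded 15.6, against the stated 82%. So the inputs are being read as intended.

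**Size of the Poisson error by hand.** Let a course last 1 + Poisson(7.06) days and let residents not differ at all. The variance-to-mean ratio of days is then (8.06² + 7.06) / 8.06 = 8.94, so Poisson standard errors are too small by √8.94 = 2.99. Simulated for the urinary-versus-respiratory interaction: 0.262 / 0.086 = 3.05. The joint interaction test at a true null then rejects with probability:

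- three types (2 df): P(χ² > 5.99 / 8.94 = 0.670) = exp(−0.335) = 72%;
- five types (4 df): P(χ² > 9.49 / 8.94 = 1.061) = exp(−0.531) × 1.531 = 90%.

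This happens with zero correlation between a resident's rows.

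**Simulated type I error of the joint Wald interaction test (nominal 5%).** 1,500 trials per three-type setting. *Clustered* means Poisson estimates with standard errors clustered on resident.

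| Setting | Poisson | Negative binomial | Clustered |
|---|---|---|---|
| Days, 3 types, 8-day courses, shared frailty variance 0 / 1 / 2 | 71 / 73 / 73% | 0.2 / 0.0 / 0.1% | 5.7 / 5.7 / 5.3% |
| Days, 3 types, exact negative binomial margins (variance 2), within-resident correlation 0 / 0.44 / 0.89 | 66 / 51 / 5% | 4.4 / 0.9 / 0.0% | 5.1 / 6.0 / 6.1% |
| Days, 5 types, 8-day courses | 88–94% | 3–16% | 4–7% |
| Episodes, 3 types, shared frailty variance 0.5 / 1 / 2 | 5.2 / 3.9 / 6.0% | 3.2 / 1.1 / 0.8% | 5.7 / 4.7 / 6.9% |
| Episodes, 3 types, type-specific frailty variance 1, none shared | 12.7% | 4.7% | 5.3% |

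With 5–11-day courses, a shared frailty and added type-specific frailty, the Poisson figure for three types reaches 83–86%.

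**What correlation between rows does to negative binomial.** With exact negative binomial margins, its standard error for the urinary-versus-respiratory interaction stays at 0.262, while the true SD falls from 0.254 (correlation 0) to 0.196 (0.44) and 0.087 (0.89). The arm effect averaged over types goes the other way: standard error 0.109 against a true SD of 0.151 and 0.180, so type I error is 15% and 24%. Clustering gives 6% and 5%. With 8-day courses and three types, the misfit of the negative binomial variance dominates instead, and the averaged effect is conservative (0.3–3%).

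**Power.** If the probiotic halves urinary antibiotic days and changes nothing else (three types), negative binomial finds the interaction in 5–11% of trials and clustered standard errors in 39–64%.

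**Type-specific effects.** With exact negative binomial margins, the respiratory arm effect has standard error 0.183 against a true SD of 0.177–0.186 at every correlation.

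**The case against.** The strongest reply is that the table gives one line per outcome, never says the models are single-level, and leaves variance estimation to a statistical analysis plan that is not shown. That is fair as to intent. It does not remove the point: a model is named for each row, and the table states nesting where its authors wanted it, so a reader who follows the table would fit the model without it.

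A second reply is that gross over-dispersion would trigger the fallback in section 18.1, so the Poisson result would not be reported. That also has weight, although the table keeps Poisson as the main analysis. The fallback then carries the problem, because its own interaction test can be far from nominal in either direction.

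Third, a reader might infer that the repeated rows cause the 70–85% error. They do not: the rate is 67–80% with no within-resident correlation at all. In those settings plain robust standard errors without clustering also come close (2–5%). The part that belongs to the repeated rows is the behaviour of negative binomial with correct margins, shown above.

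Fourth, the objective in section 5.1 is the effect within each infection type. Those effects do not depend on correlation between a resident's rows. That stands, and it limits the harm to the interaction test and to effects averaged over types.

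**Conclusion.** The point holds in a limited form. For antibiotic days by infection type, neither listed model gives a dependable interaction test. Poisson rejects a true null about 70–85% of the time with three types and multi-day courses. Negative binomial ranges from about 0%, with a large loss of power, to 16%, depending on the number of types and the shape of the data.

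Three stronger readings are not supported:

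- That the negative binomial test would almost always find nothing. This fits three types, but section 18.2 lists five, where it rejects 3–16%.
- That both rows are equally harmed. For site-of-infection episodes under a shared frailty, the Poisson interaction test is near nominal (4–6%) and negative binomial mildly conservative (1–3%). Poisson rises to about 13% only when the frailty is type-specific.
- That the trial's main result is at risk. These are secondary outcomes; the primary analysis and sample size are unaffected.

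The sizes rest on assumed frailties, course lengths and shares for the two rare types. The Poisson error also shrinks if all extra variation is shared within residents (51% at correlation 0.44, 5% at 0.89). The need to name a suitable variance does not depend on any one of these values.

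**What to change.** In both arm-by-type rows of section 18.2, state that standard errors are robust and clustered on participant, with a small-sample correction. This handles the over-dispersion and the repeated rows together and can be used with the Poisson mean model already named. The correction is there because clustered tests can be slightly liberal at this size (up to about 7%).

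The cost is one phrase per row and one software option, with no new data and no change to the sample size. A participant random effect alone was not tested here, so it should not be taken as an equivalent remedy. An offset for days observed is a separate matter.

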## 4 Introduction

### 4.1 Background

#### ***Introduction***

The PRINCESS trial will evaluate the efficacy and mechanisms of a nutritional intervention (daily probiotics) on (i) cumulative antibiotic administration days (CAAD) for all-cause infections and (ii) incidence and duration of infections in care home residents. Antibiotic prescribing has been found to be associated with isolation of resistant organisms and subsequent infections that are resistant to antibiotics. Fewer and less severe infections may reduce the need for antibiotics in CHR. This may therefore reduce the driving influence on AMR and may reduce the likelihood of subsequent resistant infection.

Care home residents (CHR) are particularly vulnerable to common infectious diseases (CID) (1) which are the commonest cause of hospitalisation in this group, costing the NHS >£54 million/year, and often results in lasting health decline. Frailty, atypical presentation and bacterial colonisation patterns lead to high antibiotic use. Reducing antibiotic prescribing in the expanding care home sector is central to the challenge of containing antimicrobial resistance (AMR) in UK.

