
Thus, while both of the proposed probiotic strains have never been evaluated for the purposes intended in the PRINCESS trial; there is evidence from other population groups that these strains have the effect of reducing frequency, severity and duration of infections and stabilising bowel flora. Many infections in the elderly result in autoinoculation from the bowel. It could be likely that the two strains may supplement each other in terms of efficacy due to different mode of actions.

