### 5.1 Primary and secondary objectives and outcome measures

	Objectives	Outcome Measures	Timepoint(s)* of evaluation of this outcome measure
Primary	To evaluate the effect of a daily dose of oral probiotics on cumulative systemic antibiotic administration days (CAAD) for all-cause, acute infections	CAAD for all cause infections; Total number of days of systemic antibiotic administration as recorded in care home medical records and discharge summaries if the participant is admitted to hospital	Over a 12* month period (data recorded at regular intervals by RN from care home records)
Secondary	To determine the effect of daily probiotic intake;		
Infection	On CAAD for the following sub-categories of infection; respiratory tract infections (RTI), urinary tract infections (UTI), skin infections, gastrointestinal infections (GI), unexplained fever and other	Total number of days of antibiotic administration for each infection type as recorded in care home medical records (collect generic name and mode of delivery) (to be recorded as defined daily dose multiples)  Number, site, duration (mean and cumulative) of infection.	Over a 12* month period (data recorded at regular intervals by RN from care home records)
	On incidence and duration of diarrhoea in CHR who are being treated with oral antibiotics	Estimation of incidence and duration of all cause diarrhoea in CHR when taking (and also not taking) oral antibiotic treatment  Estimation of incidence and duration of antibiotic-associated diarrhoea in CHR when taking oral antibiotic treatment	Question asked by RN and recorded on weekly record sheet  Question asked by RN and recorded on weekly record sheet

	The site, incidence and duration of infection (RTI, UTI, skin infection, GI and unexplained fever)  On prevalence of C. difficile infection (clinical and bacteriological evidence of C. difficile colonisation)	Stool sample laboratory analysis	Over a 12* month period (data recorded at regular intervals by RN from care home records)  At baseline, 3* and up to 12* months
Health Utility	On participants health utility	Self and/or proxy reported health related quality of life measurement EQ5D (5L)	At baseline, 3* and up to 12* months
Wellbeing	On participants wellbeing	Self and/or proxy reported ICEpop CAPability measure for Older people (ICECAP-O)	At baseline, 3* and up to 12* months

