### **Adherence-adjusted analysis**

While our primary analyses will be conducted using the intention-to-treat principle (i.e. a comparison of groups as randomised regardless of what happens after randomisation), we will monitor adherence to study product throughout the trial. Using this data, we will perform adherence-adjusted analyses, deriving estimates of treatment efficacy that maintain a comparison of groups as randomised, using structural mean models (50). A definition of adherence to study product will be defined prior to the commencement of any statistical analysis.

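### Mean episode duration is compared only among episodes that occurred, so the hazard ratio is not a comparison as randomised and can be biased in either direction

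*Protocol*

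**What the plan says.** The table in Protocol section 18.2 gives the main analysis of mean duration of infection as "A two-level Cox PH (frailty) model with infections nested within participants". The row for mean duration of diarrhoea episodes carries the same text, including the word infections. The sensitivity column is empty for both rows. The table footnote says that sensitivity analyses will consider adherence and missing data or deaths, which is a different matter.

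The same table has rows for "Incidence of infection" and "Cumulative number of infection days", and for incidence and cumulative days of all-cause diarrhoea. These use count regression and are not restricted to residents who had an episode. Section 5.1 lists the outcome as "Number, site, duration (mean and cumulative) of infection", so mean and cumulative duration are both intended.

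On what the product is expected to do, section 4.1 names "incidence and duration of infections in care home residents" as the second of two effects to be evaluated and adds: "Fewer and less severe infections may reduce the need for antibiotics in CHR". Section 4.2 cites evidence from other populations that "these strains have the effect of reducing frequency, severity and duration of infections and stabilising bowel flora". For the primary analyses, section 18.1 explains intention-to-treat as "a comparison of groups as randomised regardless of what happens after randomisation".

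**The concern.** The unit of the Cox model is the episode. A resident with no infection contributes nothing, and a resident with several contributes several times. Whether an infection exists to be analysed is itself something the product is meant to influence. The infections compared between arms are therefore selected after randomisation by a possible treatment effect, and randomisation no longer makes the two sets alike.

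The frailty term accounts for correlation between episodes in the same resident. It does not bring back episodes that were prevented, and it does not make the remaining ones comparable.

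A hazard ratio from this row, listed as a main analysis, would naturally be read as the effect of the product on how long infections last. It can differ from 1 when the product changes the length of no infection at all. It can also hide or exaggerate a real change.

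**Working it through.** The protocol gives no planning figure for mean duration, so there is none to reproduce. The question is how far the hazard ratio moves when the product prevents some infections and leaves the length of every other infection unchanged.

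**Inputs from the protocol.**
- 2.16 antibiotic prescriptions per resident-year (section 4.2), used as a stand-in for the infection rate.
- 17.4 antibiotic days per resident-year (section 17.2), so 17.4 / 2.16 = 8.06 days per course, used as a stand-in for infection length.
- 258 residents allocated 1:1 and about 250 days of data each (sections 17.1 and 17.2). This gives 129 × 2.16 × 250/365 ≈ 191 expected infections per arm without prevention.

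**Step 1: hand illustration.** Assume half of infections last 4 days and half 12.12 days, which gives a mean of 8.06. In the probiotic arm:

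- mean per episode = Σ(share kept × length) / Σ(share kept)
- days per resident-year = 2.16 × Σ(share kept × length)

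| 20% of infections prevented | Mean per episode | Days per resident-year |
|---|---|---|
| None (placebo) | 8.06 | 2.16 × 8.06 = 17.41 |
| All short | (0.3×4 + 0.5×12.12)/0.8 = 9.08 | 2.16 × 7.26 = 15.68 |
| Unrelated to length | (0.4×4 + 0.4×12.12)/0.8 = 8.06 | 2.16 × 6.448 = 13.93 |
| All long | (0.5×4 + 0.3×12.12)/0.8 = 7.05 | 2.16 × 5.636 = 12.17 |

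The per-episode mean rises, stays the same or falls, although no remaining infection changed length. Days per resident fall in all three cases.

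**Step 2: simulation.** There were 400 simulated trials per scenario, with 258 residents and 250 days each. Assumed, and not in the protocol:
- Weibull durations with shape 1.5.
- Gamma frailty variance 0.5 for incidence and 0.3 for duration. The duration frailty raises the average length from 8.06 to about 9.7 days.
- Short means under 7 days.

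The fitted model was a Weibull proportional hazards model with gamma frailty, a parametric stand-in for the frailty Cox model. A hazard ratio (HR) for resolution below 1 reads as longer infections. The last column is the ratio of cumulative infection days, probiotic to placebo.

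| Prevented | HR | Mean days, placebo vs probiotic | HR below 1 | Significantly longer | Significantly shorter | Cumulative-days ratio |
|---|---|---|---|---|---|---|
| None | 1.003 | 9.76 vs 9.74 | 51% | 4.0% | 8.0% | 0.988 |
| 10%, random | 1.005 | 9.76 vs 9.74 | 50% | 8.5% | 6.5% | 0.894 |
| 10%, all short | 0.906 | 9.75 vs 10.41 | 72% | 17.0% | 1.8% | 0.951 |
| 20%, random | 0.995 | 9.74 vs 9.75 | 52% | 6.5% | 4.5% | 0.786 |
| 20%, all short | 0.790 | 9.72 vs 11.27 | 94% | 34.5% | 0.3% | 0.924 |
| 20%, all long | 1.252 | 9.75 vs 8.42 | 9% | 0.3% | 34.0% | 0.694 |

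Monte Carlo error on the percentages is about 2 points. In the three scenarios without bias, significant results in one direction appeared in 4.0% to 8.5% of trials, where 2.5% is nominal. The simulated test is therefore somewhat liberal, and the 17% and 34% figures should be read against that background.

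**Step 3: sensitivity to the duration assumption.** A second simulation used 132 residents per arm, gamma durations with coefficient of variation 0.6 rounded up to whole days (mean about 8.6), and a Cox model for resolution. It ran 60 trials per scenario. With 20% prevented, all of 7 days or less, the hazard ratio was 0.86 and mean duration went from 8.6 to 9.5 days. With prevention unrelated to length it was 1.00. The direction agrees with Step 2, but the size does not.

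**The case against.** **The direction is not known.** A reader might infer that the product will look as if it lengthens infections. The protocol does not support that. It nowhere says that short infections are the ones prevented, and section 4.2 expects reductions in frequency, severity and duration together. Prevention unrelated to length gives no bias, and prevention of long infections gives the opposite bias. This objection stands, and the point is therefore limited to bias in either direction.

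**A true shortening could offset apparent lengthening.** That is so, but the estimate would still be wrong. In the hand illustration, an assumed true shortening of 10% combined with 20% of infections prevented, all short, gives 9.08 × 0.9 = 8.17 days against 8.06. A real benefit would disappear.

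**The safeguard is already in the table.** Incidence and cumulative days are planned over all residents, and cumulative days pointed the right way in every prevention scenario. This largely stands and is why the remedy is cheap. The two Cox rows are still listed as main analyses with nothing to mark them as conditional. A reader might go further and infer that the plan contradicts itself between these rows. It does not: length per episode and total days per resident are different quantities and may properly diverge.

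**The sizes are fragile.** This stands. A prescription rate is used as an infection rate, antibiotic days as infection length, and the all-short and all-long scenarios are extremes. In the hand illustration, 20% of all infections is 0.2/0.5 = 40% of the short ones.

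**The as-randomised statement in section 18.1 concerns the primary analyses.** This is correct, so no breach of the stated principle for the primary outcome is alleged.

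**The diarrhoea wording is a slip.** A reader might infer that the row does not model diarrhoea at all. Its label is clear, and the word infections is evidently carried over from the row above.

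**Conclusion.** The point holds for two secondary rows. The per-episode Cox hazard ratios for infection and diarrhoea compare sets of episodes formed after randomisation, so they are not treatment comparisons as randomised, and the participant frailty does not change that.

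The direction of bias depends on which episodes are prevented, which the protocol does not say. With 20% of infections prevented, the hazard ratio for resolution was 0.79 to 0.86 if all were short, about 1.00 if unrelated to length, and 1.25 if all were long. With 10% prevented, all short, it was 0.91. These figures assume no change in the length of remaining infections and rest on duration distributions that the protocol does not give. The possible directions do not depend on those distributions, but the sizes do.

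The primary outcome, cumulative antibiotic administration days, is unaffected.

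**What to change.** In Protocol section 18.2, or in the analysis plan that implements it:

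1. Base the treatment conclusion about duration on cumulative infection days and cumulative diarrhoea days per randomised resident, counting zero for residents without an episode, and read these together with incidence. All of these rows already exist.
2. Keep the per-episode frailty Cox results as descriptive, labelled as conditional on having an episode, without a causal treatment claim.
3. In the row for mean duration of diarrhoea episodes, replace infections with diarrhoea episodes as the unit nested within participants.

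The cost is wording only, with no new data and no change to sample size. What is given up is the status of the per-episode hazard ratio as a treatment comparison.
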